Comparison of Preoperative Ultrasound Guided Nerve Blocks to Intraoperative Nerve Block Catheters for Breast Reconstruction: A Prospective Randomized Trial

NCT03201809

6/21/2018

PROTOCOL TITLE:

1) Protocol Title

Title: Comparison of Preoperative Ultrasound Guided Nerve Blocks to Intraoperative Nerve Block Catheters for Breast Reconstruction: A Prospective Randomized Trial

Protocol Version Date: 6/21/18

2) Objectives

Aim 1: Report the efficacy and safety of pectoralis nerve blocks for breast reconstruction surgery in a prospective fashion

- Hypothesis: we anticipate >90% efficacy of all pectoralis nerve blocks and no complications

Aim 2: Comparison of intraoperative versus preoperative placement of pectoralis nerve blocks

2A: Comparison of block efficacy and safety

- Hypothesis: We anticipate a significantly better block efficacy with intra-operatively placed block catheters as opposed to pre-operatively placed blocks, as intra-operatively placed blocks are done under direct visualization and can be left in place. We anticipate no difference in safety profile.

2B: comparison of secondary outcomes, such as cost, block placement time, post-op nausea/vomiting, patient satisfaction, and operative times.

- Hypothesis: We anticipate a faster overall time (From admission to clearance for PACU discharge) with intra-operatively placed blocks. We anticipate use of less inhalational anesthesia with pre-operatively placed blocks. We anticipate no difference in secondary outcomes, such as post-operative nausea and vomiting, narcotic use and patient satisfaction between the two block groups.

3) Background

Level 1 data shows improved post-operative analgesia with decreased anesthetic and opiate use, decreased hospital length of stay, and improved patient satisfaction scores with the use of regional nerve blockade.¹⁻⁵ Using nerve blocks to limit general anesthesia (GA) and improve post-operative analgesia is additionally important due to the mounting evidence that volatile anesthetics and opioid analgesics impair immune function^{6,7}, and increase the risk of ileus, thromboembolism and myocardial infarction⁸. Despite these advantages, the use of regional nerve blockade is still limited to selected cases.

Pectoral nerve (Pecs) blocks are ultrasound guided inter-fascial plane blocks that target the tissue planes between the pectoralis major and minor (Pecs I), and pectoralis minor and serratus anterior muscles (Pecs II)^{9,10}. Targeting these planes with local anesthetic blocks the medial and lateral pectoral nerves, anterior divisions of the thoracic

PROTOCOL TITLE:

intercostal nerves from T2-T6, long thoracic nerve, and thoracodorsal nerves providing analgesia to the anterior and lateral thoracic walls with an extension into axilla. Pecs blocks have shown excellent efficacy in post-operative analgesia after breast surgery¹¹. The main disadvantages of the traditional Pecs blocks are the need for ultrasound trained personnel, increased anesthesia wait times as well as the need for a secondary procedure. Placement of the blocks under direct visualization addresses these limitations of and may allow more accurate plane targeting.

This research will be significant to the fields of anesthesia/pain management, breast surgery and plastic surgery. With this study, we hope to provide objective, prospective data on pectoralis nerve block efficacy and safety. We furthermore hope to examine the differences between blocks placed by anesthesia and catheter based blocks placed intra-operatively by the surgical team, as listed above under Aims.

2. Pei L, et al. Ultrasound-Assisted Thoracic Paravertebral Block Reduces Intraoperative Opioid Requirement and Improves Analgesia after Breast Cancer Surgery: A Randomized, Controlled, Single-Center Trial. 2015; 10: e0142249.

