
6) Study Endpoints

The primary study endpoint will be after completion of study (after surgery and survey completion) of 252 patients (126 in each treatment arm). Secondary endpoints include time to PACU clearance and time to hospital discharge. Because the intervention is a single-shot injection, there are no specific safety endpoints. Please see below for a discussion of potential adverse from the pectoralis nerve blocks.

7) Procedures Involved

Subjects presenting for immediate breast reconstruction and meeting inclusion criteria will be approached pre-operatively to make them aware of the study. On the day of surgery, patients will be asked to sign consent for the study. Patients who sign consent will then undergo randomization to a study arm (pre-op placement of intra-op catheter placement). Randomization will be done by study personnel using the i-phone application “Randomizer.” Randomization will follow a blocked scheme; that is, if one patient is randomized to the anesthesia block group, the next will automatically get the catheter treatment. This will ensure equal numbers in both study arms. After consent and randomization is complete, patients will be told of their study arm. Patients will then be asked to fill out a pre-operative pain survey discussing their baseline level of breast pain.

For those randomized to the pre-op placement arm, anesthesia will perform this block prior to surgery but after their pre-operative survey is complete. The anesthesia

PROTOCOL TITLE:

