department is already performs pectoralis nerve blocks on selected patients, and have the work flow set up for this. The dose will be 10 mL of 0.25% Ropivacaine for the pecs 1 injection, and 20 mL of 0.25% Ropivacaine for the pecs 2 injection. Ropivacaine is a standard sodium channel blocking anesthetic already FDA approved for peripheral nerve blocks. For those randomized to the intra-operative arm, catheter placement will be performed after the pectoralis muscle flap has been raised, for more accurate targeting of the tissue planes and nerves. Blocks will be performed by the operating surgeon. Instead of single shot blocks, a commercially available On-Q nerve block catheter (Halyard Health, Alpharetta, Georgia) will be placed. Through these catheters, 0.2% Ropivacaine will be instilled at 4 mL/hr for a total of 400 mL (amount in standard On-Q reservoirs). Vitals are continuously monitored in the operative suite and in the Post Anesthesia Care Unit (PACU), with a high level of supervision by the anesthesiology team. In the very rare event of an adverse reaction to the injection, appropriate action will be taken immediately and in accordance with standard work-flow for local anesthetic toxicity (epinephrine for severe allergy or circulatory support, intravascular lipid emulsion and sodium bicarbonate for overdose, although our doses should not be high enough to precipitate this, even with inadvertent intravascular injection). If hypoxia not due to opioids and not responsive to supplemental oxygen is present, a chest radiograph will be ordered to rule out pneumothorax from inadvertent visceral pleural puncture.

Post-operatively, the patients will be monitored in the PACU. They will have standard anesthesia pain and nausea management orders written for (these are ordered en bloc as part of an already existing order set). PACU nursing staff will dose medications according to the written orders. PACU clearance time (which is currently time-stamped in the chart by the PACU resident) will be noted. Often patients will remain in PACU due to ward over-crowding, so actual time of PACU discharge will not be noted. Post-PACU hospital course will proceed as is standard of care, with PRN pain and nausea medication ordered. Standard hospital discharge criteria will be used for all groups.

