With respect to the surveys, Redcap is a mature, secure web application that has been used successfully by many other investigators at our institution to collect secure survey data.

Data analysis will be done using <http://vassarstats.net>. Statistical comparisons will be performed across the study groups using T-test for two-group comparisons.

All research personnel will be up to date with their HIPAA training.

For our power analysis, we set our alpha = 0.05 and beta (power) = 0.8. Using the Bashandy et al. paper¹, the mean morphine requirement in the PACU was 2.9 ± 1.861 mg for the Pecs block group, and 6.9 ± 1.861 mg for the control group ($p < 0.001$). Based on our preliminary experience with pre-operatively placed pecs blocks, we estimate that they work well about 70% of the time. If we hope to see a 20% improvement with more accurate plane targeting, then our average morphine requirement in the intra-operative placement group would be 2.3 mg. Therefore, we would have to enroll 126 patients in each arm to have an 80% chance of seeing a difference, if there truly is one.

9) Provisions to Monitor the Data to Ensure the Safety of Subjects

The EMR of every subject who completes the injection portion of this study will be assessed within 24 hours of pectoralis nerve block placement. Any untoward events, such as intravascular injection, allergic reaction, pneumothorax or other unanticipated event will be assessed for its causative relationship to the pectoral nerve block . We anticipate these to all be very unlikely, as the current literature on the pectoralis nerve blocks report a 0% complication rate (see citations, above). If a serious adverse event occurs, these will be reported immediately to the IRB and will be a trigger for an immediate suspension in enrollment and a review of the injection protocol with the Chiefs of both the Departments of Anesthesiology and Surgery. If any performer error can be identified and corrected, then with approval from the departments enrollment will continue. If not, the study will be terminated.

We will cumulatively review the data after 20 subjects in each study arm have been enrolled, and then again at 50 patients, 75 patients, 100 patients, and 126 patients.

10) Withdrawal of Subjects

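### Aim 2 and the power rationale speak of placement and plane targeting, but the arms compare two whole strategies, and the reason given for having no safety endpoints does not fit the catheter arm

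*Combined protocol and SAP*

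**What the plan says.** All references are to the combined protocol and SAP.

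**How the question is framed**
- Section 2 (Objectives) heads Aim 2 "Comparison of intraoperative versus preoperative placement of pectoralis nerve blocks".
- Hypothesis 2A expects better efficacy from the catheters, "as intra-operatively placed blocks are done under direct visualization and can be left in place". It expects no difference in safety.
- Section 8, in the power paragraph, writes "If we hope to see a 20% improvement with more accurate plane targeting" and from there reaches a mean PACU morphine requirement of 2.3 mg, against 2.9 mg for the pre-operative block. It names no other source for the improvement.
- The title sets ultrasound-guided blocks against nerve block catheters. Section 3 (Background) sets blocks given by anesthesia against catheter-based blocks placed by the surgical team.

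**What the arms are (Section 7)**
- Pre-operative arm: "anesthesia will perform this block prior to surgery", with "10 mL of 0.25% Ropivacaine for the pecs 1 injection, and 20 mL of 0.25% Ropivacaine for the pecs 2 injection".
- Intra-operative arm: "Instead of single shot blocks, a commercially available On-Q nerve block catheter" is placed by the operating surgeon, and "0.2% Ropivacaine will be instilled at 4 mL/hr for a total of 400 mL".

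**Safety**
- Section 6: "Because the intervention is a single-shot injection, there are no specific safety endpoints".
- Section 9 has each patient's record assessed within 24 hours of block placement.
- Section 7 has catheters removed at about post-operative day 4 or 5.
- Section 11 names catheter-related infection as an additional risk.

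**The concern.** The protocol states two different questions. One is whether a surgeon-placed catheter infusion does better than an ultrasound-guided single shot. The other is whether placing the block during surgery, under direct vision, targets the plane better. The design can answer the first but not the second, yet the Aim 2 heading and the power paragraph are worded for the second.

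What is at stake is the conclusion. A catheter advantage on the day 2 to 7 pain surveys could come from continued infusion with no gain in targeting. A catheter disadvantage in the PACU could come from slow early delivery despite perfect targeting. Neither result would test the mechanism that the power paragraph relies on.

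The same mismatch affects safety. Aim 2A promises a safety comparison, but the stated reason for having no safety endpoints describes only one of the two arms.

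**Working it through.** **1. The plan's own figures.** The assumed catheter mean is 2.9 × (1 − 0.20) = 2.32 mg, which the plan rounds to 2.3 mg. The assumed difference is therefore 0.58 mg (0.6 mg after rounding), with SD 1.861 mg. Using n per arm = 2 × (z for alpha + z for power)² × SD² / difference², with a 0.58 mg difference and 80% power:
- one-sided alpha 0.05: 2 × (1.645 + 0.842)² × 3.463 / 0.336 ≈ 128, close to the stated 126;
- two-sided alpha 0.05: 162.

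The plan does not state sidedness. That is a separate matter, and nothing below depends on it. What matters here is that the full 0.58 to 0.6 mg is credited to targeting.

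**2. What changes between the arms (Section 7).**

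| Feature | Pre-operative arm | Intra-operative arm |
|---|---|---|
| Timing and guidance | before surgery, ultrasound | after the muscle flap is raised, direct vision |
| Operator | anesthesia | operating surgeon |
| Delivery | single shot, 0.25% | catheter infusion, 0.2% |

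These are three distinct bundles. Concentration, duration and total dose all belong to the delivery bundle and should not be counted as further independent factors.

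**3. Size of the delivery difference, as written.**
- Single shot: (10 + 20) mL × 2.5 mg/mL = 75 mg.
- Infusion rate: 4 mL/h × 2 mg/mL = 8 mg/h.
- Infusion duration: 400 mL / 4 mL/h = 100 h.
- Infusion total: 400 mL × 2 mg/mL = 800 mg; 800 / 75 = 10.7.

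**4. The contrast reverses over time.**
- Time for the infusion to deliver 75 mg: 75 / 8 = 9.4 h.
- By 24 h: 24 × 8 = 192 mg; 192 / 75 = 2.6 times the single shot.
- At the PACU assessment, assuming 1 to 4 h of infusion (the documents give no figure): 8 to 32 mg, or 11% to 43% of 75 mg.

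The catheter arm has thus had less drug than the other arm when the powered outcome is measured, and more from about 9.4 h onward. These figures take the text literally. Per-side dosing, the number of catheters and any initial bolus are not stated, and each could change them.

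**5. What the analysis can separate.** The stated method is a t-test between two groups. Each of the three bundles takes one value in every patient of an arm, so it coincides exactly with the arm. Covariate adjustment could not separate them either.

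**6. Safety passages side by side.** Section 6 calls the intervention a single-shot injection; Section 7 says the catheter replaces the single shot. The Section 6 reason therefore fails for 126 of 252 patients. A record review within 24 hours of placement covers at most 24 of the 100 infusion hours, so at least 76 h of infusion, and any later time until removal, fall outside it.

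**The case against.** The strongest reply is that the protocol already knows it is comparing packages. The title names catheters. The Background names both operator and delivery mode and ties them to the Aims. Hypothesis 2A gives leaving the catheter in place as one of its two reasons, and that is the infusion component. The Aim 2 heading is a label. The targeting phrase only motivates an effect size, and deleting it changes no mean, SD, sample size or test. No endpoint or reporting rule commits the investigators to a mechanistic conclusion.

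Most of this stands, and it limits the point to the Aim 2 heading and the power paragraph. It does not remove it. The power paragraph names targeting as the only source of the improvement, and the heading states a contrast that was not randomised on its own.

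Four stronger readings are tempting but not supported:
- *That the comparison is invalid.* Randomising patients between two complete strategies is legitimate.
- *That the protocol credits timing and targeting throughout.* Hypothesis 2A, the title and the Background say otherwise.
- *That the catheter arm has a 10.7-fold dose advantage on the powered outcome.* That ratio builds up over 100 h. In the PACU the literal figures run the other way.
- *That the sample size must change.* Nothing here depends on it.

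It may also be said that Section 6 is a different defect. It is, and it is treated separately here. Section 11 does discuss catheter infection, and Section 9 adds cumulative data reviews at intervals of enrolment. Neither passage sets out how catheter events are to be collected after the first 24 hours.

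**Conclusion.** The point holds in a limited form. The trial can estimate the effect of one strategy against the other. It cannot attribute a difference, in PACU morphine or in any later outcome, to placement timing, direct vision or plane targeting, because operator and delivery regimen change with them. The delivery difference alone is large: 75 mg once against 8 mg/h for 100 h, subject to the unstated details on sides, catheters and bolus. The PACU comparison of 8 to 32 mg with 75 mg also rests on the assumed 1 to 4 h of infusion.

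Separately, the Section 6 statement contradicts Section 7 for half of the planned patients. It leaves the 2A safety comparison resting mainly on a 24-hour record review, while catheters stay in until about day 4 or 5. These passages must be reconciled.

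**What to change.** 1. Restate Aim 2 and Hypothesis 2A as a comparison of two strategies: *pre-operative ultrasound-guided single-shot block by anesthesia versus intra-operative surgeon-placed catheter infusion*.
2. In the power paragraph, present the 20% reduction (2.9 to 2.3 mg) as the assumed effect of the catheter strategy as a whole, and remove targeting as its sole source.
3. Add one sentence saying that differences will be reported as strategy effects and not attributed to timing, operator or targeting.
4. State whether the volumes and rates in Section 7 are per side, how many catheters are used and whether any bolus is given, so that the two strategies are fully described.
5. Reconcile Section 6 with Sections 7, 9 and 11. Define how catheter-related events such as infection will be recorded in the safety comparison for as long as the catheter is in place.

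Items 1 to 4 are wording and change neither the arms nor the sample size. Their price is a narrower mechanistic claim. Item 5 adds a small amount of data collection, which could be done at the post-operative appointment where catheters are already to be removed.

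### The no-difference hypotheses for safety, nausea and vomiting, narcotic use and satisfaction have no analysis that could support them, and the narcotic-use one conflicts with the basis of the sample size

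*Combined protocol and SAP*

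**What the plan says.** All references are to the combined protocol and SAP.

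- **Section 2, Aim 2A**, under a hypothesis label, expects significantly better block efficacy with intra-operative catheters. On safety it adds: "We anticipate no difference in safety profile".
- **Section 2, Aim 2B**, also under a hypothesis label: "We anticipate no difference in secondary outcomes, such as post-operative nausea and vomiting, narcotic use and patient satisfaction between the two block groups".
- **Section 8**, on analysis: "Statistical comparisons will be performed across the study groups using T-test for two-group comparisons". No other comparative method is named. The document gives no confidence interval, margin, equivalence test or non-inferiority test for any outcome.
- **Section 8**, on power, starts from a published trial in which "the mean morphine requirement in the PACU was 2.9 ± 1.861 mg for the Pecs block group". It applies a hoped-for 20% improvement, so that "our average morphine requirement in the intra-operative placement group would be 2.3 mg", and arrives at 126 per arm for an 80% chance of detecting the difference.
- **Section 6** describes the primary endpoint as completion of 252 patients. It names no outcome variable as primary and says there are no specific safety endpoints.
- **Section 7** collects opioid use in morphine equivalents for the operating room and for the first 6, 12, 18 and 24 hours after surgery. It collects nausea and vomiting as an incidence.
- **Section 9** handles safety through record review within 24 hours, a causality assessment of each event, suspension of enrollment after a serious adverse event, and cumulative reviews. It states no criterion for comparing the arms.

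**The concern.** There are two linked problems.

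First, a test for a difference can give evidence that the arms differ. Failing to reject does not show that they are alike, because a non-significant result also arises when the sample is too small or the outcome too variable. To support a no-difference statement, a plan needs an interval to be judged against a stated margin. This plan has neither.

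Second, the plan points two ways on opioids. Aim 2B expects narcotic use not to differ, while section 8 sizes the trial to detect a fall in PACU morphine, which is a narcotic-use measure. With no outcome variable named as primary, nothing says which expectation governs. A null opioid result would be a failure to find the effect the trial was built to detect, yet it would agree with a stated hypothesis.

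At stake is whether the trial can honestly say that the two techniques are alike on safety, nausea and vomiting, and satisfaction, and how a null opioid result would be interpreted.

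**Working it through.** **Inputs from the documents.** Section 8: SD 1.861 mg; means 2.9 and 2.3 mg (difference 0.6 mg as printed; an exact 20% of 2.9 is 0.58 mg); 126 per arm; "we set our alpha = 0.05 and beta (power) = 0.8", read as power 0.80. Sidedness is not stated.

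**Assumed inputs.** The documents give no nausea and vomiting rate, so 20–40% is assumed. They give no margin, so 10 points is assumed for illustration.

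**1. The plan's own figure.** n per arm = 2 × [SD × (z_α + z_0.80) / difference]².
- 0.6 mg, two-sided: 2 × [1.861 × (1.960 + 0.842) / 0.6]² → 152.
- 0.6 mg, one-sided: 2 × [1.861 × (1.645 + 0.842) / 0.6]² → 119.
- 0.58 mg, two-sided → 162.
- 0.58 mg, one-sided → 128.

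The stated 126 is approached only by the one-sided calculation with the unrounded 0.58 mg, so both readings of sidedness are carried forward.

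**2. Chance that the opioid comparison misses a real difference.** The standard error is 1.861 × √(2/126) = 0.234 mg.
- At 0.6 mg, power from the noncentral t is 72.2% two-sided and 81.8% one-sided. Misses are therefore 28% and 18%.
- Smaller true differences, two-sided, normal approximation: 0.45 mg is missed 52% of the time and 0.3 mg 75%.
- The 95% interval half-width is 1.96 × 0.234 = 0.46 mg, about three-quarters of the target (0.46 / 0.6 = 0.77).

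**3. Nausea and vomiting at 126 per arm.** The half-width for a common rate p is 1.96 × √(2p(1−p)/126). The miss rate is for a two-sided 5% comparison of two proportions when the true rates are p and p + 10 points. The last column is the n per arm needed to show equivalence within 10 points by two one-sided tests with 80% power and no true difference: 2p(1−p)(1.645 + 1.282)² / 0.10².

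| Assumed p | 95% half-width | Miss rate, +10 points | n per arm, 10-point margin |
|---|---|---|---|
| 20% | 9.9 points | 55% | 275 |
| 30% | 11.3 points | 62% | 360 |
| 40% | 12.1 points | 64% | 412 |

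At 20% the half-width is already about the size of the assumed margin, and at 30% and 40% it exceeds it.

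**4. Safety.** If one arm of 126 has no events, the upper limit of the exact two-sided 95% interval for that arm's rate is 1 − 0.025^(1/126) = 2.9%. This bounds a single arm and is not an interval for the difference between arms.

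**5. The two opioid statements against each possible result.** A significant fall in PACU morphine with catheters agrees with section 8 and contradicts 2B if 2B covers that measure. A non-significant result agrees with 2B. A significant rise contradicts both.

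**The case against.** The strongest reply is that these are expectations about secondary outcomes, not equivalence objectives. The text says what the investigators anticipate, secondary outcomes need not be powered, and the 2.3 mg figure is a conditional sizing value. That is fair as far as it goes. But the statements carry the same hypothesis label as the superiority prediction in 2A, and the plan supplies nothing else by which to judge them. The point asks for no extra power, only that the claim match what the data can show.

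Several stronger readings are tempting, and the documents do not support them.

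- *Any opioid result would confirm one of the two statements.* It would not: significantly higher use in the catheter arm contradicts both.
- *Safety will be decided by a non-significant t-test.* The t-test sentence names no safety variable, and section 9 sets out case-by-case review. What is missing is a between-arm criterion for the 2A statement.
- *The sponsor will report p > 0.05 as proof of similarity.* Nothing in the text says so. The defect is that the plan neither rules this out nor offers an alternative.
- *Aim 2B and section 8 concern one identical variable.* Section 8 uses morphine in the PACU; 2B refers to narcotic use generally, and section 7 collects it over several intervals. The measures overlap and need reconciling, but they are not shown to be the same.
- *The trial misses its target effect 28% of the time, without qualification.* That holds for a two-sided test; one-sided it is 18%.

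**Conclusion.** The point stands. The plan contains no analysis that could support its no-difference hypotheses, and this conclusion needs no outside figure. The conflict over opioids is also real, because PACU morphine falls within narcotic use and no primary outcome variable settles which expectation governs.

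The opioid miss rates rest on the plan's own SD and effect, with the range reflecting the unstated sidedness. The figures for nausea and vomiting rest on the assumed 20–40% rate. The zero-event bound applies to one arm only.

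This should be corrected before analysis. It leaves treatment and data collection untouched but changes what the trial may conclude.

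**What to change.** - Reconcile section 2 with section 8: state which opioid measure, over which interval, is the efficacy (superiority) outcome, and remove that measure from the no-difference list in 2B. State the sidedness of its test.
- For safety and the remaining 2B outcomes, report each between-arm difference with a 95% confidence interval, using a difference in proportions for nausea and vomiting and for complications.
- State that p > 0.05 will not be taken as evidence of no difference.
- Claim similarity only where the interval lies within a margin fixed, with its clinical justification, before analysis.

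The cost is a few sentences and intervals computed from data already being collected. The downside is that some no-difference statements will become inconclusive. The similarity route is not free either: 126 per arm could rarely support a tight margin, since an assumed 10-point margin for nausea and vomiting would need about 275–412 per arm. For most of these outcomes, estimation without a similarity claim is the realistic choice.
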